If a subject experiences any of the risks described above, they will be asked to report it as soon as possible to the research team. Skin irritations, electrical burns, and electrical shocks will be assessed and treated by the study physician if necessary. In the event of skin irritations associated with the electrodes, alternative electrodes may be used and/or the use of the stimulator may be temporarily suspended. In the event of uncomfortable sensations associated with the electrical stimulation, the stimulus parameters will be readjusted to the subjects' comfort. In the event of electrical burns, the subject will be retrained in the procedures necessary to guard against their occurrence. In the event of electrical shocks, the equipment will be assessed for faults. All equipment has been designed to minimize the possibility of electrical hazards. All study staff will be informed how to reach appropriate medical personnel should an adverse event occur during treatment or assessment sessions.

Participants will be instructed in how to contact study personnel or the appropriate on-call physician should an adverse event occur while at home. There are no known lasting side effects associated with undergoing an MRI examination. Procedures in place for protecting against and minimizing potential risks include the presence of software constraints that limit the maximum deposited RF energy and the maximum magnetic gradient flux. This is a safeguard that is imbedded within the operating system of the MR imager, and will provide the same level of safeguard to the patient in this research study as is present in a conventional clinical MR examination. Therefore, these parameters will be

within the FDA guidelines that have been developed to pose no risk to human subjects. The potential risks are also minimized by careful subject selection, excluding any patient with a contraindication to MRI (e.g. the presence of ferromagnetic metal in body, pacemaker, pregnant) from the pool of eligible subjects, and excluding any patient with a history of claustrophobia to prevent subject anxiety. To further limit any potential for discomfort, time in the scanner will be less than 1 hour. Subjects will wear noise-damping headphones to reduce exposure to MRI noise well below the FDA limit. A microphone in the headphones will allow the subject to communicate with the examiner in an emergency if he/she wants to be removed from the scanner at any time. The risk of maintaining data security will be minimized by keeping data locked in the investigators' offices and by following HIPAA regulations.

In addition to the risk management for the study described above, subjects will be given a group-specific user's manual that describes how to use the stimulator safely. This will be reviewed with each subject before they are sent home with the stimulator. The manual will list the following safety precautions:

SAFETY PRECAUTIONS:

- Avoid handling the electrodes while the stimulator is on. Always remember to turn off the stimulator before you remove the electrodes.
- Place electrodes on the skin only where instructed
- Never position electrodes on the chest, across the heart, or on the neck.
- Do not place electrodes over broken skin as this may cause a skin irritation.
- Do not submerge the stimulator in water.
- Do not use the stimulator in the bathtub or shower
- Do not operate dangerous machinery or drive while using the stimulator.
- Do not sleep while using the stimulator. Remain attentive during use to avoid skin burns.
- Use new electrodes if the reused ones no longer stick to the skin.
- Always wash and dry the skin before applying the electrodes.

- A slight reddening of the skin under the electrode is normal. This should fade after 1 hour once the electrodes are removed. If you notice redness or blistering beyond this, discontinue use and contact study personnel.
- Do not participate in this study if you are pregnant or may be pregnant; the safety of electrical stimulation in pregnancy has not been determined.
- Electrical stimulation should not be used by patients with implanted electronic devices (cardiac demand pacemakers etc.) unless under specialized medical supervision.
- Do not participate in this study if you have a history of potentially fatal cardiac arrhythmias.
- Electrical stimulation should not be used by people who have poorly controlled epilepsy.
- The stimulator has been programmed specifically for the intended user only. Do not let others use the stimulator.

Statistical Analysis Plan

We hypothesize that the CCFES+HTVG group will have greater post-treatment gains than the CCFES group on upper extremity motor outcomes. Exploratory looks at the data will be done before fitting our models. The adaptive randomization should force relatively good balance of potential confounding variables (e.g., fMRI eligible, severity of impairment, time post-stroke), but imbalances in treatment adherence or any other baseline covariate (e.g., lesion location, etc.) or adherence may still require their inclusion as covariates. Each measure will be modeled using a linear mixed effects approach which is well-suited for handling correlated repeated measurements, unbalanced data, and missing data and dropouts in longitudinal studies, while permitting us to control for potential confounders.¹ Least square (LS) means will be calculated using model estimates and adjusted for missing values for each group at each time point. This approach allows comparisons and estimates of treatment group effects at any time point, and also allows comparisons and estimates across time points within groups to evaluate the persistence or decay of the treatment effect. Secondarily, we hypothesized that participants who were less than 2 years after stroke or had moderate hand impairment at baseline would improve more than participants who were more than 2 years after stroke or had severe hand impairment at baseline. A mixed effects modeling analysis will be used similar to the primary analysis to evaluate the effects of time post-stroke and impairment severity. For fMRI data, differences from baseline to EOT in beta coefficient maps for each region of interest will be evaluated with paired t-tests and cluster threshold set to >100 voxels. Between-group comparisons will be made with independent t-tests.

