Contralaterally Controlled FES plus Video Games for Hand Therapy after Stroke

NCT03058796

Study Protocol and Statistical Analysis Plan

Note: The text below was extracted from the IRB protocol for this study, which was first approved on February 9, 2017. The most recent amendment to the protocol was approved on:

August 8, 2019

Study Protocol

Abstract

Objectives: This study will determine the effect of integrating two promising therapy modalities for improving upper limb function after stroke, hand therapy video games (HTVG) and contralaterally controlled functional electrical stimulation (CCFES). It is expected that CCFES+HTVG will enhance the motor impairment and functional outcomes achieved by CCFES alone. Secondarily, we will evaluate the effect of baseline impairment and time post-stroke on treatment response, and explore the effects of CCFES+HTVG vs. CCFES alone on cortical activity during a hand task (fMRI assessment).

Research Plan: This is a randomized controlled trial in which stroke patients will be assigned to either CCFES+HTVG or CCFES for 12 weeks. Hand dexterity, upper limb impairment, and upper extremity activity limitation will be evaluated by a blinded assessor at 0 (baseline), 3, 6, 9, 12 (end of treatment), 24, and 36 weeks. Cortical activation will be assessed at 0 and 12 weeks.

Methodology: Up to 52 stroke survivors with chronic (> 6 months) upper extremity hemiplegia will be enrolled and randomized. The two groups will receive equivalent doses of treatment over a 12 week period consisting of 10 sessions per week (7.5 hrs) of self-administered treatment at home plus 2 sessions per week (3 hrs) of group-specific occupational therapy in the lab. The home sessions for the CCFES+HTVG group will consist of CCFES-mediated video game play according to instructions provided during the lab sessions. For the CCFES group, the home sessions will consist of CCFES-mediated hand opening exercise. The lab sessions for both groups will consist of a period of observation and instruction regarding the home sessions followed by CCFES-mediated functional hand task practice.

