Clinical Significance: This study will demonstrate the supplemental motor relearning value of virtual reality/video games to CCFES therapy, (2) identify patients most likely to respond to both therapies, and (3) determine whether adding HTVG to CCFES simply enhances cortical activation underlying CCFES or engages additional cortical areas to improve response across broader ranges of severity and chronicity. This study is an important step toward the development and dissemination of new

treatments that may be applicable and effective across a wide range of patients who have lost hand function after stroke.

Specific Aims

AIM 1: Determine the effect of integrating Hand Therapy Video Games (HTVG) with Contralaterally Controlled Functional Electrical Stimulation (CCFES) on upper extremity motor outcomes

Hypothesis 1: Stroke patients treated with CCFES+HTVG will have greater and faster improvements in hand dexterity, upper limb impairment, and activity limitation than those treated with CCFES alone

AIM 2: Evaluate the effect of baseline impairment and time post-stroke on treatment response

Hypothesis 2: Compared to CCFES, CCFES+HTVG will benefit patients with greater baseline impairment and time elapsed post-stroke.

AIM 3: Explore the effects of CCFES+HTVG vs. CCFES on cortical activation during a hand task

Hypothesis 3: Compared to CCFES, CCFES+HTVG will exhibit greater re-mapping in the brain, demonstrated as greater lateralization of activity, greater recruitment of learning- based networks in ipsilesional and contralesional regions, and increased intensity of cortical activity.

Methods and Procedures

General Study Design

A single-blinded randomized controlled trial will be carried out to assess the effects of 12 weeks of CCFES+HTVG compared to CCFES. Dexterity, upper limb impairment, and activity limitation will be assessed at 0 (baseline), 3, 6, 9, 12 (end of treatment), 24, and 36 wks. Cortical activation (measured with fMRI) will be optionally assessed at 0 and 12 wks. The treatment dose will be the same for both groups: 10 sessions per week (7.5 hrs) of self-administered treatment at home plus 2 sessions per week (3 hrs) of group-specific occupational therapy in the lab.

Device

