Stimulation is delivered through standard self-adhering pre-gelled 2"x2" square and 1.25" round electrodes (e.g., PALS®, Axelgaard Manufacturing, Fallbrook, CA). The analog input source for the stimulator is an assembly of three passive bend sensors 1/4" wide by 4 1/2 " long (Spectra Symbol, Salt

Lake City, UT) which are either attached by Velcro or inserted through slits cut into the top of the index, middle, and ring fingers of an athletic glove.³ The sensors act as variable resistors. When the fingers open and close, the electrical impedance of each sensors changes; these impedance changes are supplied as the analog input to the stimulator. The stimulator is programmed to produce current pulses with pulse widths (intensities) that are proportional to input from the glove worn on the nonparetic hand.

The CCFES+HTVG system uses a bend sensor that is worn on a finger of the paretic hand to detect opening and closing. The sensor is attached to a fingerless “glove” and plugs into an analog-to-digital converter module, which in turn plugs into a USB port on a 17-inch touchscreen laptop computer. The computer is an all-in-one unit that requires no other components besides the monitor’s touchscreen (no keyboard or mouse) to select and play the games. The computer is configured so that it can only be used for the game play prescribed to the participant and requires a USB key from the investigators to run.

Randomization

Subjects will be assigned to a treatment group using an adaptive randomization algorithm⁵ to minimize group imbalances on 4 key patient characteristics: (1) time post-stroke (< 2 yrs vs. \geq 2 yrs), (2) baseline motor status (moderate vs. severe), (3) paretic side (dominant vs. non-dominant),⁶ and (4) fMRI eligibility (yes vs. no). Patients with $\geq 10^\circ$ active wrist extension, 10° active thumb abduction/extension, and 10° active extension in at least two additional digits will be considered to have “moderate” impairment, and patients with less movement than that who meet all the other motor criteria (see Section 30) will be considered to have “severe” impairment.⁷

Device Set Up

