- demonstrate ability to follow instructions for operating the stimulator or have a caregiver who will assist them.

Exclusion criteria:

- co-existing neurologic diagnosis of peripheral nerve injury, Parkinson's disease, spinal cord injury, traumatic brain injury, or multiple sclerosis
- uncontrolled seizure disorder
- severely impaired cognition and communication
- uncompensated hemineglect
- arm or forearm skin breakdown or edema (to avoid edema-related shunting of current)
- insensate forearm (to avoid risk of electrical burns)
- history of potentially fatal cardiac arrhythmias
- implanted electronic systems (e.g. pacemaker)
- botulinum toxin injections to any upper extremity muscle within 3 months of enrolling
- pregnant women due to unknown risks of surface NMES during pregnancy
- participating in occupational therapy or other rehabilitation therapies to the upper extremity
- severe shoulder or hand pain

Exclusion criteria related to fMRI procedures include:

- implanted metal devices (e.g., cardiac pacemaker or defibrillator, hemostatic clips, nerve stimulators, insulin pumps, lead wires, cochlear implant, prosthetic heart valve, etc.) or indwelling metal that is incompatible with MRI (e.g., metal splinters in the orbit)
- claustrophobia
- pregnancy

Stroke survivors who do not meet the fMRI-related selection criteria but who do meet the rest of the criteria may still participate in the study, but not the fMRI procedures.

Potential Risks

Skin Irritation – When surface electrodes are used, it is possible that the subject will experience a temporary redness of the skin from either the electrodes, the conductive gel used with them, or any adhesive used to secure them. Skin irritation and redness from the electrical stimulation is also possible, but this possibility is rare and minimized by the type and intensity of stimulation that will be used. Participants will be instructed that redness should fade within an hour and that if redness persists, they should contact study staff. If necessary, electrodes or adhesives will be replaced with an alternative.

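### Allocation is balanced on fMRI eligibility, but Aim 3 compares only subjects who are actually scanned, so balance in that set is not guaranteed

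*Combined protocol and SAP*

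**What the plan says.** The Randomization section uses an adaptive algorithm "to minimize group imbalances on 4 key patient characteristics". The fourth of these is given as "4) fMRI eligibility (yes vs. no". The fMRI-related exclusions under Selection Criteria are incompatible metal or implants, claustrophobia and pregnancy; willingness to be scanned is not among them. The same section adds: "Stroke survivors who do not meet the fMRI-related selection criteria but who do meet the rest of the criteria may still participate in the study", though without the fMRI procedures.

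On the scan itself, General Study Design states: "Cortical activation (measured with fMRI) will be optionally assessed at 0 and 12 wks". The Abstract has no such qualifier: "Cortical activation will be assessed at 0 and 12 weeks".

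General Study Design also states: "A single-blinded randomized controlled trial will be carried out". The assessor is the blinded party, and subjects will know whether they were given video games.

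The Statistical Analysis Plan says of the fMRI data: "differences from baseline to EOT in beta coefficient maps for each region of interest will be evaluated with paired t-tests". Arms are then compared by independent t-tests, with no covariates named. The same section expects the adaptive randomization to balance potential confounders, and gives fMRI eligibility as an example.

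**The concern.** Eligibility, consent to be scanned and possession of usable scans are three different things. The algorithm balances the first, while Aim 3 is analysed in the last. An eligible subject who declines is coded yes in the algorithm and contributes nothing to the fMRI comparison.

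Timing is the second issue. Eligibility and motor status must be known before allocation because they are inputs to it. The available text does not say the same of the fMRI opt-in or the week-0 scan. Calling that scan baseline suggests that it comes before treatment, which is not the same as before allocation. If the decision to be scanned follows allocation in subjects who know their arm, the scanned groups could differ for reasons other than chance.

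The planned analysis has no second line of defence. The mixed model's provisions for covariates and missing data are not extended to the fMRI t-tests, and neither a comparison of scanned with unscanned subjects nor a rule for a missing scan is given. Aim 3 carries a directional between-arm hypothesis, so the comparability of the scanned groups matters to it.

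**Working it through.** The plan gives no figure to reproduce: no size for the fMRI subset, no eligible share and no opt-in rate. The only sample-size input is "Up to 52 stroke survivors with chronic (> 6 months) upper extremity hemiplegia will be enrolled and randomized". Every rate below is an assumption, used to show a range.

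**1. Numbers scanned, with opt-in unrelated to arm.** Assume 60% or 80% of 52 are eligible (31 or 42), split as evenly as possible between arms, and 60% or 80% of those opt in. The number scanned in each arm (n1, n2) is then binomial. The variance of a two-group comparison relative to an even split of the same total is (1/n1 + 1/n2) / (4/(n1 + n2)).

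| Eligible | Opt-in | Expected scanned | P(arms differ by 4 or more) | Mean variance factor |
|---|---|---|---|---|
| 31 | 60% | 31 × 0.6 = 18.6 | 0.21 | 1.027 |
| 31 | 80% | 31 × 0.8 = 24.8 | 0.14 | 1.010 |
| 42 | 60% | 42 × 0.6 = 25.2 | 0.27 | 1.018 |
| 42 | 80% | 42 × 0.8 = 33.6 | 0.17 | 1.006 |

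The average loss is about 1-3% of variance, and the 95th percentile reaches about 10% in the worst of these cases.

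**2. The same question with the allocation simulated.** The type of algorithm and its assignment probability are not stated. I assumed marginal (Pocock-Simon) minimisation, four binary factors with the other three at 50% prevalence, a biased coin of 0.8, and 2,000 runs per scenario.

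| Opt-in among eligible | Mean absolute arm difference in number scanned | P(4 or more) |
|---|---|---|
| 100% (scanned set is the balanced set) | 1.3-1.4 | 0.05-0.07 |
| 80% in both arms | 2.1-2.3 | 0.18-0.23 |
| 60% in both arms | 2.3-2.7 | 0.23-0.30 |
| 80% versus 50% by arm | 4.7-6.3 | 0.66-0.81 |

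The mean absolute arm difference in the share at one level of motor status was about 0.045 in all randomised, 0.07-0.11 in the eligible, and 0.10-0.17 in the scanned when opt-in was incomplete. Marginal minimisation does not balance the other factors within a subset, so part of this would remain even with full uptake.

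**3. Opt-in that depends on arm.** With 15.5 or 21 eligible per arm, opt-in of 80% in one arm gives 12.4-16.8 scanned, and 60% in the other gives 9.3-12.6: about 12-17 against 9-13. Unequal counts alone do not bias a t-test; a difference in composition can. Suppose the eligible are half moderate and half severe. Opt-in of 80% among moderate and 50% among severe subjects in one arm gives a moderate share of 0.8/(0.8 + 0.5) = 62%. Opt-in of 65% in both strata of the other arm gives 0.65/(0.65 + 0.65) = 50%. If the 80%/50% pattern held in both arms, both shares would be 62%, with no systematic difference between arms.

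So opt-in unrelated to arm adds chance imbalance only. Systematic bias needs opt-in, or later loss, whose pattern differs by arm.

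**The case against.** A reader might infer that the scanned subset is unbalanced and that subjects choose scanning according to their arm. The documents do not support that. If nearly all eligible subjects are scanned, the numbers stay balanced. No section describes a choice about scanning made after allocation, and no reason is given why willingness to have a baseline scan should differ by arm. The consent pages, where an optional procedure would normally be explained, were removed from the public text, so its silence on timing is not evidence that the order was left open. The word optionally may mean no more than that ineligible subjects skip the scan, which would agree with the Abstract, and sites may already count willingness as part of eligibility.

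It can also be said that the plan names fMRI eligibility as a potential confounder and never states that the factor is there to balance the scanned set. The factor does serve that stated purpose.

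Finally, Aim 3 is exploratory, the precision loss is small, and the size of any bias in an fMRI outcome cannot be worked out from the documents. The post-randomisation week-12 scan is a clearer route to arm-dependent loss than the baseline scan, and no change to the allocation factor reaches it.

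All of this stands as a limit on the point. What remains is that the listed criteria do not include willingness, the scan is called optional, and the between-arm fMRI test is unadjusted. On the available text, the factor does not secure balance in the set analysed.

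**Conclusion.** The point holds in a limited form: balance on eligibility does not guarantee balance among those scanned, and the available text leaves arm-dependent opt-in possible without documenting it. It does not show that imbalance or self-selection by arm occurs.

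The gain in precision from fixing it is small, about 1-3% of variance on average, under assumed eligibility of 60-80% and assumed opt-in of 60-80%. The main benefit is to protect the exploratory Aim 3 comparison from selection at baseline. The primary Box and Blocks comparison does not depend on who is scanned. The change is worth making because it is cheap and because selection into the scanned set is hard to repair by analysis afterwards.

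**What to change.** - Redefine the fourth factor as eligible for and consented to fMRI (yes or no), or as baseline fMRI obtained (yes or no), and state that the opt-in and the baseline scan are completed before allocation. If this is already the practice, it only needs writing down.
- Reconcile the Abstract with General Study Design on whether the scan is optional, and for whom.
- The analysis of change needs the week-12 scan too, and its loss is not covered by any allocation factor. Report scan uptake, completion of both scans, and baseline characteristics of those scanned, by arm.
- Adjust the between-group fMRI comparison for the allocation factors in place of the unadjusted t-test.

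The cost is one changed algorithm input, one sentence on visit order, and modest additions to analysis and reporting, with no new procedure. The practical downside is that allocation waits for the baseline scan in those who opt in, and that scan is off site: scanning is at the Cleveland Clinic and the therapist-guided sessions are at the LSVDVAMC.

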Activation will be examined in motor cortices bilaterally: primary motor cortex (M1), premotor cortex (PMC), and supplementary motor area (SMA), and in other areas, all of which will be outlined using a standard AFNI atlas as in our previous studies to reduce subjectivity that arises from manually drawing regions around the area of the infarct. For each region, active voxels represent the raw volume of activation or "voxel count". The likelihood of cortical lesions affecting our analysis will be reduced by excluding false positive activation found in infarcted regions. The following indices will be derived to quantify functional re-mapping.

Laterality Index: Since our previous work and that of others have found that activation shifts to predominantly ipsilesional motor cortices with significant gains in dexterity, we will study whether the balance of activation between ipsi- vs. contralateral M1, S1 and PMC shifts to the ipsilesional hemisphere with greater recovery.¹⁸⁻²¹ Voxel counts will be normalized by comparing *between* the two hemispheres using a laterality index that is calculated as follows.^{18,19,22,23} Laterality index = (I - C) / (I + C), where I = the active voxel count in the ipsilesional hemisphere and C = the active voxel count in the contralateral hemisphere. The range of possible values is -1 (entirely contralateral activation) to +1 (entirely ipsilesional activation). Laterality of brain activity during movement of both the paretic

and non-paretic hands will be studied, providing a strong within-subject control. Although the brain activation during non-paretic hand movement cannot be considered "normal", it offers a reasonable method of normalizing and investigating recovery within and across subjects.

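### The laterality index compares raw active-voxel counts with no adjustment for cortex lost to infarction, and the SAP assigns it no baseline-adjusted test

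*Combined protocol and SAP*

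**What the plan says.** The protocol's fMRI Metrics section takes its regions from an atlas: they are "outlined using a standard AFNI atlas as in our previous studies to reduce subjectivity". The number of active voxels in a region is used as a raw volume. The Laterality Index paragraph then defines "Laterality index = (I - C) / (I + C), where I = the active voxel count in the ipsilesional hemisphere", with C the corresponding count on the other side, applied to M1, S1 and PMC. It treats this comparison between hemispheres as the normalisation of the counts. On lesions, it says their influence will be reduced by "excluding false positive activation found in infarcted regions". It states no removal of the mirror region, no denominator of surviving tissue and no lesion-volume adjustment. The index is also taken during movement of the non-paretic hand, as a within-subject control.

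Under Selection Criteria, both cortical and subcortical first strokes are eligible. Under Randomization, the four balancing factors are time post-stroke, baseline motor status, paretic side and fMRI eligibility.

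Hypothesis 3 expects greater re-mapping with CCFES+HTVG, "demonstrated as greater lateralization of activity" being its first element. For fMRI the Statistical Analysis Plan says that "differences from baseline to EOT in beta coefficient maps for each region of interest will be evaluated with paired t-tests", and then that between-group comparisons use independent t-tests. It does not mention the laterality index. Lesion location appears as an example of a baseline imbalance that may need a covariate; lesion size does not appear.

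**The concern.** A count ratio between hemispheres normalises properly only if both sides have the same amount of tissue able to activate. After a cortical infarct in M1, S1 or PMC they do not. I is then lower because tissue is missing, whatever the surviving tissue does, and C is untouched. Two patients with the same activation per unit of living cortex get different index values, and the same physiological shift gives them different changes in the index.

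At stake is the arm comparison behind the lateralization part of Hypothesis 3. Lesion extent is not balanced by design, and fMRI is optional within a trial of at most 52 patients, so a chance difference in lesion extent between the scanned groups is plausible. An independent t-test takes no covariate, so it cannot absorb such a difference. It is also not stated whether that test would be applied to the week-12 value or to the change, and the two differ in how much of the lesion effect they carry.

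**Working it through.** **Inputs from the documents.** The index formula, its use of raw counts, its stated range of −1 to +1, and the two visits (0 and 12 weeks).

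**Assumed inputs.** f, the fraction of the ipsilesional region lost, taken as the same at both visits; r, the ratio of ipsilesional to contralesional activation density in living tissue; and regions of equal size before the stroke. The documents give no values for f or r.

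**Check of the plan's own figure.** Evaluating (I − C)/(I + C) over all integer pairs from 0 to 200 gives a minimum of −1 and a maximum of +1, as stated. The index is undefined only at I = C = 0.

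**Formula with tissue loss.** I is proportional to (1 − f)r and C to 1, so

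LI = ((1 − f)r − 1) / ((1 − f)r + 1).

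**Level at r = 1, and change when r rises from 0.5 to 1**

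| f | LI at r = 0.5 | LI at r = 1 | Change |
|---|---|---|---|
| 0 | −0.333 | 0 | +0.333 |
| 0.25 | −0.455 | −0.143 | +0.312 |
| 0.50 | −0.600 | −0.333 | +0.267 |
| 0.75 | −0.778 | −0.600 | +0.178 |
| 0.90 | −0.905 | −0.818 | +0.087 |

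Example at f = 0.50, r = 1: (0.5 − 1)/(0.5 + 1) = −0.333.

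**Direction of the distortion.** It is not always a shrinkage. For r from 2 to 4 the change is 0.600 − 0.333 = +0.267 at f = 0 and 0.333 − 0 = +0.333 at f = 0.50. For any fixed f below 1 the index rises with r, so the sign of a change is kept. If r does not change, the index does not change.

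**What a chance imbalance would do.** Suppose every patient in one arm had f = 0.25 and every patient in the other f = 0.50, with r going from 0.5 to 1 in both. A comparison of week-12 values would show −0.143 − (−0.333) = 0.190. A comparison of changes would show 0.312 − 0.267 = 0.045. Neither reflects a difference in re-mapping.

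**Does the non-paretic hand cancel it?** Take, before loss, I = 200 and C = 200 for the paretic hand and I = 100 and C = 300 for the non-paretic hand (assumed counts). The paretic minus non-paretic difference is:

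- f = 0: 0 − (−0.500) = 0.500
- f = 0.50: −0.333 − (−0.714) = 0.381
- f = 0.75: −0.600 − (−0.846) = 0.246

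It still depends on f.

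**After the correction.** Dividing I by the non-infarcted voxels in its region replaces (1 − f)r by r, so LI = (r − 1)/(r + 1). At r = 1 this is 0 for every f below 1, and the change for r from 0.5 to 1 is +0.333 for every f below 1.

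**The case against.** Much can be said in the plan's defence.

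- The exclusion step is sound. Activation in dead tissue is spurious, and dropping it corrects I. A reader might infer that the protocol deletes cortex from one hemisphere and so creates the asymmetry. The text does not say that; missing tissue lowers I with or without the step.
- Strokes that spare M1, S1 and PMC have f = 0 and are unaffected.
- Patients are more than 6 months post-stroke, so f is reasonably taken as constant between visits. A lesion imbalance then cannot by itself produce a change in the index. It only rescales a real one, and in the example above the arms' changes differ by just 0.045.
- The SAP allows imbalanced baseline variables to enter as covariates. That provision sits with the mixed models, however; the fMRI sentences specify t-tests.
- The independent t-test sentence can be read to cover the index. So it goes too far to say that no test exists: the gap is that none is tied to the index and that the one offered is unadjusted.

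A reader might also infer that undefined or extreme values will be common and will remove mainly severe patients. The documents do not support this. The remark about participants with little or no finger movement explains how the track is scaled and says nothing about voxel counts. The index is undefined only when both counts are zero and equals ±1 only when exactly one is zero; I = 2, C = 3 gives −0.2.

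**Conclusion.** The point holds in limited form. The raw-count index varies in level with the share of ipsilesional cortex lost: from 0 to −0.60 as f goes from 0 to 75% at equal density. The size of its change varies as well: +0.33 down to +0.18 over the same range for r from 0.5 to 1, and in the other direction at higher ratios. The planned non-paretic-hand control does not remove this, and lesion size is neither a balancing factor nor a named covariate.

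A reader might take this as a systematic bias in favour of one arm. It is not: under randomisation it is added noise and possible chance imbalance, of unknown size and sign. All lesion fractions and density ratios here are assumptions. Aim 3 is exploratory, fMRI participation is optional, and no motor outcome depends on the index. The change is still worth making, because lateralization leads Hypothesis 3 and the remedy is cheap.

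**What to change.** 1. In the SAP, name the test of the lateralization claim: the week-12 laterality index compared between arms by ANCOVA, with the baseline index as covariate, in place of an unadjusted independent t-test. This uses scans already planned and adjusts for chance differences in baseline level, including those due to lesion extent.
2. In fMRI Metrics, compute I and C as active voxels divided by non-infarcted voxels in each atlas region, with the same activation threshold at both visits. Report the raw-count index as a sensitivity analysis.

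The second step removes f exactly only if the lost tissue would have activated at the same density as the rest of the region; otherwise it is an approximation. Replacing counts by an unthresholded sum of positive betas is not advised, because noise from inactive voxels pulls the index towards zero. With an assumed 10% of ipsilesional and 5% of contralesional voxels active, true beta 1 and voxel noise SD 1, a density index of 0.333 falls to about 0.04.

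The cost is a few sentences, a little code, and some work to record infarct extent within the regions. The documents do not say that lesion masks exist, but excluding activation in infarcted tissue already requires locating the infarct. Comparison with the group's earlier count-based indices becomes slightly less direct, which the sensitivity analysis covers.
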